5.2.2 Withdrawal of subjects from the follow-up period

Subjects *must* be withdrawn from the study follow-up period for the following reasons:

- Patient lost to follow up.
- At any time during the study and without giving reasons, a subject may decline to participate further. The subject will not suffer any disadvantage as a result.
- At the discretion of the investigator.

5.2.3 Replacement

A subject withdrawn from study treatment will not be replaced.

5.3 Subject identification

Subject will be identified by a 3 digit number beginning with 001, sequenced consecutively.

6. Treatments

6.1 Treatments to be administered

The following investigational products will be used in this study:

- Regorafenib, 40 mg tablets
- COVERSYL® (perindopril erbumine) 4 mg.

Stivarga® will be used as per the marketed indication (“on label”), Coversyl® will be used off-label and as such a Clinical Trial Application will be filed with Health Canada.

COVERSYL® (perindopril erbumine) 4 mg will be administered daily for 21 days of a 28-day cycle. Perindopril will be administered orally, first thing in the morning on an empty stomach.

Regorafenib will be administered 160 mg daily for 21 days of a 28-day cycle. Regorafenib will be administered with low fat breakfast, one hour after perindopril. A low fat breakfast as defined by the Stivarga® (regorafenib) Product Monograph is one that is <30% fat, ~300-550 calories. See Appendix 14.4.

Table 1: Treatment Plan

Phase II Study of Perindopril and Regorafenib in mCRC (PARICCA)

Drug	Dose	Administration Guidelines
Perindopril	4 mg daily*	Administered orally on an empty stomach first thing in the morning.
Regorafenib	160 mg daily	Administered orally, one hour after waking with a low fat breakfast.

Caution with use of potassium sparing diuretics.

Caution for development of hypotension with diuretics.

BSC includes any concomitant medications or treatments: antibiotics, analgesics, radiation therapy for pain control (limited to bone metastases), corticosteroids, transfusions, psychotherapy, growth factors, palliative surgery, or any other symptomatic therapy necessary to provide BSC, except other investigational anti-tumor agents or anti-neoplastic chemotherapy.

Patients will continue study treatment until disease progression or they meet the criteria in Section 5.2. The dose modifications will follow the pre-defined dose levels outlined in Section 6.4.

6.2 Identity of study treatment

The regorafenib 40 mg tablet contains regorafenib and the inactive excipients microcrystalline cellulose, croscarmellose sodium, magnesium stearate, povidone, colloidal anhydrous silica, Polyvinyl alcohol-part hydrolyzed, Talc, Titanium dioxide - E 171 (color index 77891), Macrogol/PEG 3350, Lecithin (Soy), Iron oxide yellow - E172 (color index 77491), Iron oxide red - E 172.

The perindopril 4 mg tablets contains perindopril erbumine 4g, as well as Chlorophyllin (E141ii) Aluminium Lake, hydrophobic colloidal silica, lactose monohydrate, magnesium stearate, microcrystalline cellulose. Each light green, rod shaped breakable tablet engraved with  on one face and scored on both edges contains: perindopril erbumine 4 mg. pills are available in blister packs of 30 tablets and in bottles of 100 tablets.

6.3 Treatment assignment

N/A – all patients in this single-arm trial will receive treatment with regorafenib and perindopril.

6.4 Dosage and administration

6.4.1 Perindopril

COVERSYL® (perindopril erbumine) 4 mg will be administered daily for 21 days of a 28-day cycle. Perindopril will be administered orally, first thing in the morning on an empty stomach. If a dose is missed, a double dose should not be taken, but just carry on with the next dose at the normal time.

The Investigator or designated study personnel is responsible for dispensing the study drug to patients.

6.4.2 Regorafenib

Regorafenib will be administered 160 mg daily for 21 days of a 28-day cycle. Regorafenib will be administered with low fat breakfast, one hour after perindopril. A low fat breakfast as defined by the monograph¹⁰ is one that is <30% fat, ~300-550 calories (see appendix 14.4).

The rationale for the dose in this study is based upon the phase I data from Study 11650 (in which escalating doses from 10 mg to 220 mg of regorafenib were administered on a discontinuous schedule [3 weeks out of every 4]) and same dose and schedule have been used in Study 14387 (including Asian subjects).

Signs of anti-tumor activity were observed in subjects receiving doses from 60 mg up to 220 mg per day on a discontinuous schedule (3 weeks out of every 4). However, of the 220 mg/day cohort, 8 out of 12 subjects required a dose reduction for toxicity, whereas only 1 subject of 12 on the 160 mg/day cohort required such a dose reduction. Thus, based upon the efficacy and toxicity data, 160 mg was chosen as the dose for this study.

Dose administration

Regorafenib will be orally administered. The Investigator or designated study personnel is responsible for dispensing the study drug to patients.

Regorafenib should be taken in the morning with approximately 8 fluid ounces (240 mL) of water. The study drug should be administered after a light (<30% fat) breakfast. Some examples of low-fat breakfasts are provided in Appendix 14.4.

If a dose of regorafenib is missed, the subsequent dose of regorafenib should not be doubled. The investigator should be informed if the dose of regorafenib taken exceeded the scheduled dose.

Dose modification and delays

(Note that this confidential information comes from Bayer's CONCUR study protocol (integrated protocol v2.0, dated 28Dec2012).

Phase II Study of Perindopril and Regorafenib in mCRC (PARICCA)

Doses of study drug may be delayed or reduced in case of clinically significant hematologic and other toxicities that are possibly, probably or definitely related to protocol therapy.

Toxicities will be graded using the NCI Common Terminology Criteria Version 4.2.

The modifications of regorafenib will follow the following pre-defined dose levels:

Table 2: dose modifications for regorafenib

Dose level 0 (standard dose)	160 mg po od	4 tablets of regorafenib, 40 mg-tablet,
Dose level -1	120 mg po od	3 tablets of regorafenib, 40 mg-tablet,
Dose level -2	80 mg po od	2 tablets of regorafenib, 40 mg-tablet,

If a subject experiences several toxicities and there are conflicting recommendations, the recommended dose adjustment which reduces the dose to the lowest level should be used.

Table 3 outlines dose adjustments for toxicities related to study drug except hand-foot skin reaction, hypertension and liver function test (ALT and AST) abnormalities. **Table 4** outlines the suggested dose reductions for HFSR while **Table 5** outlines suggested dose reductions for treatment-emergent hypertension. **Table 6** outlines the suggested dose reductions for ALT and/or AST increases related to study drug.

If reduction by more than two dose levels is required, treatment will be discontinued.

If a dose reduction has been performed, intra- subject dose re-escalation can be considered (up to the maximal 160 mg daily dose) at the discretion of the treating physician provided that the toxicity (ies) has resolved to baseline.

Table 3: Dose Modification/Delay for Toxicities Related to Study Drug (Except Hand Foot Skin Reaction, Hypertension, AST and ALT)^a

Grade of Event (CTCAE version 4.03)	Dose Interruption	Dose Modification	Dose for Subsequent Cycles
Grade 0-2	Treat on time	No change	No change

Phase II Study of Perindopril and Regorafenib in mCRC (PARICCA)

Grade 3	Delay until \leq Grade 2 ^b	Reduce 1 dose level	If toxicity remains \leq Grade 2, dose re-escalation can be considered at the discretion of the treating investigator. If dose is re-escalated and toxicity (\geq Grade 3) recurs, institute permanent dose reduction.
Grade 4	Delay until \leq Grade 2 ^b	Reduce by 1 dose level. Permanent discontinuation can be considered at treating investigator's discretion.	

a Excludes alopecia, non-refractory nausea/vomiting, non-refractory hypersensitivity, non clinical significant and asymptomatic laboratory abnormalities.

b If no recovery after a 4-week delay, treatment will be permanently discontinued.

In addition to these recommended dose modifications, subjects who develop diarrhea, mucositis, anorexia or other events predisposing to fluid loss or inadequate fluid intake should be carefully monitored and rehydrated as clinically necessary. This is in order to minimize the risk of postural hypotension and renal failure.

Skin Toxicity Grade (according to CTCAE version 4.03 "Palmar-plantar erythrodysesthesia syndrome")	Occurrence c	Suggested Dose Modification c
Grade 1: Numbness, dysesthesia, paraesthesia, tingling, painless swelling, erythema or discomfort of the hands or feet which does not disrupt the subjects normal activities	Any	Maintain dose level and institute immediately supportive measures for symptomatic relief
Grade 2: Painful erythema and swelling of the hands or feet and/or discomfort which affects the subject's normal	1st occurrence	Consider decreasing dose by one dose level and institute immediately supportive measures. If no improvement, interrupt therapy for a minimum

Phase II Study of Perindopril and Regorafenib in mCRC (PARICCA)

Table 4 Dose Modifications for Hand-Foot Skin Reaction		
Skin Toxicity Grade (according to CTCAE version 4.03 "Palmar-plantar erythrodysesthesia syndrome")	Occurrence ^c	Suggested Dose Modification ^c
activities		of 7 days, until toxicity resolves to Grade 0-1. ^b
	No improvement within 7 days or 2nd occurrence	Interrupt therapy until toxicity resolves to Grade 0-1. When resuming treatment, treat at reduced dose level. ^b
	3rd occurrence	Interrupt therapy until toxicity resolves to Grade 0-1. When resuming treatment, decrease dose by one additional dose level. ^{a,b}
	4th occurrence	Discontinue therapy
Grade 3: Moist desquamation, ulceration, blistering or severe pain of the hands or feet, or severe discomfort that causes the subject to be unable to work or perform activities of daily living.	1st occurrence	Institute supportive measures immediately. Interrupt therapy for a minimum of 7 days until toxicity resolves to Grade 0-1. When resuming treatment, decrease dose by one dose level. ^b
	2nd occurrence	Institute supportive measures immediately. Interrupt therapy for a minimum of 7 days until toxicity resolves to Grade 0-1. When resuming treatment, decrease dose by one additional dose level. ^{a,b}
	3rd occurrence	Discontinue treatment permanently.
^a Subjects requiring > 2 dose reductions (< 80mg) should go off protocol therapy ^b If toxicity returns to Grade 0-1 after dose reduction, dose re-escalation is permitted at the discretion of the investigator ^c A more conservative dose modification approach, if medically indicated, is acceptable, but please contact the sponsor prior to making any changes.		

If no recovery after a 4-week delay, treatment will be discontinued permanently.

For subjects who require a dose reduction for Grade 2 or 3 rash or hand-foot skin reaction (HFSR), the dose of study drug may be increased to the starting dose after one full cycle of therapy has been administered with the reduced dose without the appearance of rash or HFSR > Grade 1.

The following measurements should be considered for prevention and treatment of HFSR:

Control of calluses

Before initiating treatment with regorafenib:

- Check condition of hands and feet
- Suggest a manicure/pedicure, when indicated
- Recommend pumice stone use for callus or 'rough spot' removal.

During regorafenib treatment:

- Avoid pressure points
- Avoid items that rub, pinch, or create friction.

Use of creams

Apply non-urea based creams liberally.e.g.:

Keratolytic Creams: Use sparingly and only to affected (hyperkeratotic) areas

- Urea-based creams
- Salicylic acid 6%

Alpha Hydroxy Acids (AHA) based creams

- Approximately 5-8% provide gentle chemical exfoliation
- Apply liberally two times each day

Topical analgesics like lidocaine 2% to be considered for pain control

Topical corticosteroids like clobetasol 0.05% should be considered for subjects with Grade 2 or 3 hand-foot skin reaction. Avoid systemic steroids.

Cushions

Protect tender areas

- Use socks/gloves to cover moisturizing creams
- Wear well-padded footwear
- Use insole cushions or inserts (e.g., silicon, gel)
- Foot soaks with tepid water and Epsom salts

Phase II Study of Perindopril and Regorafenib in mCRC (PARICCA)

Table 5: Dose modification for Treatment-Emergent Hypertension			
Grade of Event (CTCAE version 4.03)	Definition	Anti-hypertensive therapy	Regorafenib dosing
Grade 1	Pre-hypertension (systolic BP 120-139 mmHg or diastolic BP 80-89 mmHg)	None	Continue regorafenib. Consider increased blood pressure monitoring.
Grade 2	Systolic BP 140-159 mmHg or diastolic BP 90-99 mmHg OR Symptomatic increase by > 20 mmHg (diastolic) if previously within normal limits	Treat with the aim to achieve diastolic BP ≤ 90 mmHg -If BP previously within normal limits, start anti-hypertensive monotherapy -If subject already on anti-hypertensive medication, titrate up the dose	Continue regorafenib. If symptomatic, hold regorafenib until symptoms resolve AND diastolic BP ≤ 90 mmHg ^a . When regorafenib is restarted, continue at the same dose level.
Grade 3	Systolic BP ≥ 160 mmHg or diastolic BP ≥ 100 mmHg OR More than one drug or more intensive therapy than previously used indicated	Treat with the aim to achieve diastolic BP ≤ 90 mmHg -Start anti-hypertensive medication AND/OR -Increase current anti-hypertensive medication AND/OR -Add additional anti-hypertensive medications.	Hold regorafenib until diastolic BP ≤ 90 mmHg, and if symptomatic, until symptoms resolved. When regorafenib is restarted, continue at the same dose level. If BP is not controlled with the addition of new or more intensive therapy, reduce by 1 dose level ^b . If Grade 3 hypertension recurs despite dose reduction and antihypertensive therapy, reduce another dose level ^c .
Grade 4	Life-threatening consequences (e.g. malignant hypertension, transient or permanent neurologic deficit, hypertensive crisis)		Discontinue therapy

Abbreviations: BP = blood pressure; CTCAE = Common Terminology Criteria for Adverse Events, version 4.03
 
a Subjects requiring a delay of > 4 weeks should discontinue protocol therapy.
 
b If blood pressure remains controlled for at least one full cycle, dose re-escalation is permitted at the investigator's discretion.
 
c Subjects requiring > 2 dose reductions (a dose lower than 80 mg po od) should discontinue protocol therapy.
			

Phase II Study of Perindopril and Regorafenib in mCRC (PARICCA)

Blood pressure (BP) should be monitored weekly for the first 6 weeks of treatment. Blood pressure is to be recorded by qualified staff, e.g. a study nurse, treating physician, or nurse practitioner and entered onto the CRF.

The dose modification schedule for treatment emergent hypertension during regorafenib dosing should be followed (see Table 5). Subjects' BP measurements will be monitored and appropriate treatment to effectively control hypertension under regorafenib treatment is strongly recommended.

The selection of anti-hypertensive medication used in this setting should be performed at the investigator's discretion, considering possible site-specific treatment guidelines. All medication should be recorded in the subject's CRF.

Phase II Study of Perindopril and Regorafenib in mCRC (PARICCA)

Table 6: Dose modifications/interruption for ALT and/or AST increases related to study drug			
Grade of Event (CTCAE version 4.03)	1 st occurrence	Restart	Reoccurrence
AST and/or ALT baseline G0 → G1 or baseline G1 → G2	Treat on time and check AST, ALT and bilirubin 2x/week for 2 weeks followed by weekly assessments for at least 4 weeks.		Treat on time and check AST, ALT and bilirubin 2x/week for 2 weeks followed by weekly assessments for at least 4 weeks.
AST and/or ALT baseline G0 → G2	Delay until ≤ G1 and check AST, ALT, bilirubin 2x/week.	Reduce 1 dose level and check AST, ALT, bilirubin 2x/week for 2 weeks followed by weekly assessments for at least 4 weeks. ^a	Discontinue ^b
AST and/or ALT baseline any grade → G3	Delay until ≤ G1 if baseline was G0 or G1 OR until G2 if baseline was G2. Check AST, ALT, bilirubin 2x/week. If ALT or AST > 8 x ULN with a concomitant rise in bilirubin (of any degree) compared to previous bilirubin values, consider permanent discontinuation at the first occurrence ^b .	Reduce 1 dose level and check AST, ALT, bilirubin 2x/week for 2 weeks followed by weekly assessments for at least 4 weeks. ^a	Discontinue ^b
AST and/or ALT baseline any grade → G4	Discontinue ^b		

Abbreviations: AST = aspartate aminotransferase, ALT = alanine aminotransferase
 
^a If all values remain stable for 2 full cycles, dose re-escalation may be considered at the discretion of the investigator. After re-escalation AST, ALT, bilirubin should be checked 2x/week for 2 weeks, followed by weekly assessments for at least 4 weeks.
 
^b In case of discontinuation, check AST, ALT, bilirubin should be checked twice a week for 2 weeks, followed by weekly assessments until recovery to baseline.
			

During the first 2 cycles of treatment, ALT, AST and bilirubin must be monitored weekly.

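### Table 5, Grade 3 hypertension: systolic ≥ 160 alone can trigger the regorafenib hold, but only diastolic ≤ 90 releases it, so an asymptomatic patient may restart at the same dose while still in the Grade 3 pressure range

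*Combined protocol and SAP*

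**What the plan says.** All of this is in Section 6.4.2, Table 5, Grade 3 row, unless stated otherwise.

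- **Trigger.** Either pressure is enough: "Systolic BP ≥ 160 mmHg or diastolic BP ≥ 100 mmHg". A third route is the need for more treatment: "More than one drug or more intensive therapy than previously used indicated".
- **Treatment aim.** Diastolic only: "Treat with the aim to achieve diastolic BP ≤ 90 mmHg". Antihypertensives are started, increased or added.
- **Release of the hold.** "Hold regorafenib until diastolic BP ≤ 90 mmHg, and if symptomatic, until symptoms resolved". Restart is at the same dose level.
- **Next step.** "If BP is not controlled with the addition of new or more intensive therapy, reduce by 1 dose level". A further reduction follows if Grade 3 hypertension recurs. Footnote b adds: "If blood pressure remains controlled for at least one full cycle, dose re-escalation is permitted", at the investigator's discretion. Table 5 gives no numeric meaning for *controlled*.
- **Status of the table.** The text introducing Tables 3 to 6 describes the Table 5 reductions as suggested. The text after Table 5 says the schedule should be followed and strongly recommends effective control of hypertension.

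**The concern.** A hold should not be releasable by the reading that caused it. Here the trigger looks at both pressures and the release looks at one. For a patient whose diastolic pressure was never raised, the hold has no stated duration: the release condition is met when the hold begins. The treatment aim does not help, because it too is diastolic only.

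What is at stake is patient safety during an interim period. Hypertension is a known regorafenib toxicity, and Section 7.5.1.5 (expected adverse events) lists it among both the most frequent and the most serious reactions. The row permits an unchanged dose while systolic pressure is still in the range that called for interruption. How long that lasts depends partly on the next reading. From cycle 3, Section 7.1 and Table 7 schedule blood pressure only at the start of each cycle, although Section 2.2 says every second week after the first six weeks.

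**Working it through.** The plan states no figure to reproduce. The check is a comparison of conditions.

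**1. Trigger and release (pressure criteria, Table 5, Grade 3).**
- Trigger T: systolic ≥ 160 or diastolic ≥ 100.
- Release R: diastolic ≤ 90 and no unresolved symptoms.

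If R holds, diastolic is at most 90, so the diastolic limb of T is false. T and R can then both be true only through systolic ≥ 160. The overlap is exactly: asymptomatic, systolic ≥ 160, diastolic ≤ 90.

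**2. Same check with a systolic term in the release.** Let R′ be systolic < 160, diastolic ≤ 90 and no unresolved symptoms. R′ contradicts both limbs of T, so the overlap is empty. On integer readings with systolic 140–220 and diastolic 60–120, the current rule has (220 − 160 + 1) × (90 − 60 + 1) = 61 × 31 = 1,891 overlapping pairs, and R′ leaves 0. This only confirms the logic. It counts pairs of values, not patients.

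**3. Examples (assumed readings, asymptomatic patients).**

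| Reading (mmHg) | Meets T | Current rule | With systolic < 160 added |
|---|---|---|---|
| 172/84 | yes, systolic | may restart | held |
| 160/90 | yes, systolic | may restart | held |
| 172/95 | yes, systolic | held (diastolic) | held |
| 158/102 | yes, diastolic | held (diastolic) | held |
| 155/84, after a hold | no | may restart | may restart |

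The gap can also open during treatment. A patient held at 165/95 whose diastolic falls to 90 with systolic unchanged may restart at 165/90.

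**4. Does another part of the protocol close it?**
- *Table 3* delays treatment until Grade 2 or lower, but excludes hypertension.
- *Section 5.1.2* treats systolic > 150 or diastolic > 90 despite optimal management as uncontrolled. This is an entry criterion, and Section 7.1.2.2 has eligibility checked on treatment at Cycle 1 Day 1 only.
- *Section 7.1.2.2* asks a patient keeping a diary to contact the physician at systolic ≥ 150. That prompts a call and does not govern restart.
- *Section 6.4.2* lets doses be delayed for clinically significant toxicity. This is permissive.
- *Section 5.2.1* requires withdrawal if continuing would be harmful in the investigator's opinion. This sets no pressure value.

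None requires systolic pressure to fall before restart.

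**5. Size.** Section 1.2 gives severe hypertension of 7% in CORRECT and a Grade 3 figure of 11.8% in CONCUR. If those rates applied here: 34 × 0.07 = 2.38 and 34 × 0.118 = 4.01, or about 2 to 4 patients at Grade 3. Only the asymptomatic subset with systolic ≥ 160 and diastolic ≤ 90 would be affected, and the documents do not give its size.

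**The case against.** **The table is advisory and surrounded by safeguards.** The reductions are called suggested, antihypertensives are started or raised at once, and the investigator may delay dosing or withdraw the patient. The later steps also respond to systolic pressure, since recurrent Grade 3 hypertension includes systolic ≥ 160. This stands, and it limits the point. A reader might infer that the protocol compels restart at systolic ≥ 160, or leaves such patients unprotected. The documents support neither reading. What remains is that the stated default permits restart, and that the *not controlled* step changes the dose, not the condition for ending the hold.

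**It may be a deliberate rule.** Diastolic ≤ 90 is the aim and release value in the Grade 2 row as well, and Section 6.4.2 says the dose-modification material comes from the CONCUR protocol, which is not available here. That explains the origin. It does not explain why systolic pressure starts the Grade 3 hold and then drops out.

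**The other tables are an imperfect comparison.** Table 4, for example, ties restart to the grade falling: "Interrupt therapy for a minimum of 7 days until toxicity resolves to Grade 0-1". A reader might infer that hypertension should follow the same pattern. It cannot do so cleanly: a patient whose pressure is normal on two drugs may remain Grade 3 through the third criterion. The release here has to be a pressure value, and the argument rests on the mismatch within the row.

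**The rates prove little.** This is right. CORRECT used CTCAE version 3.0 and this trial uses 4.03 (Appendix 14.2), everyone here takes perindopril, and uncontrolled hypertension is excluded at entry. The figures of 2 to 4 patients are illustrative and not an upper bound.

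**Conclusion.** The point holds as a minor safety-rule correction. For asymptomatic patients with systolic ≥ 160 and diastolic ≤ 90, the Grade 3 row is entered and released on the same reading, and regorafenib may resume at an unchanged dose until antihypertensives work or the dose is reduced. Symptomatic patients stay held until symptoms resolve, and any diastolic value above 90 keeps the hold in place.

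The conclusion rests on the wording of Table 5 and on finding no systolic restart condition elsewhere. It does not rest on an estimate of frequency: the number affected is unknown and may be zero. A reader might infer that the trial's conclusions are weakened. They are not: the primary endpoint is hand-foot skin reaction of any grade, and its analysis, the sample size and the power do not depend on this rule.

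**What to change.** In the Grade 3 row of Table 5, change both the treatment aim and the release condition to: systolic BP < 160 mmHg and diastolic BP ≤ 90 mmHg. Keep the symptom condition. State that *controlled* in the dose-reduction step and in footnote b means this same pair. The Grade 2 row needs no change, because an asymptomatic Grade 2 patient continues regorafenib anyway.

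A limit of systolic ≤ 150, borrowed from the entry criterion, should not be used. It would hold a patient who has come down to 155/84 and, as not controlled, reduce the dose, while the Grade 2 row tells an asymptomatic patient with that reading to continue. The extra reductions would count toward the withdrawal rule for more than two reductions in Section 5.2.1.

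The cost is a wording amendment to one row and one footnote, with no new procedure. A few holds will last longer and count toward the 28-day interruption limit in Section 5.2.1. That limit includes the one-week break, so it allows 28 − 7 = 21 planned dosing days to be missed. Patients whose systolic pressure stays at 160 or above on intensified therapy would clearly be dose-reduced. So would those whose diastolic pressure stays above 90, which the row's existing aim already implies.
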